11.5 Cardiopulmonary function testing

11.5.1 Echocardiography is a noninvasive tool that enables the detection of cardiovascular disease as a result of radiotherapy. Echocardiography can detect pericardial disease, left ventricular systolic and diastolic dysfunction, coronary artery disease suggested by resting or stress-induced regional wall motion abnormalities, and valvular heart disease.[33] Furthermore, echocardiographic strain rate imaging, a measure of regional myocardial function, has previously been reported to detect subclinical decline in cardiac function in the anterior wall of patients treated with radiotherapy for left-sided breast cancer.[34] Echocardiography will be used to detect clinical or subclinical cardiovascular disease as a result of radiotherapy.

12.0 Descriptive Factors

- Breast Quadrant: upper inner, upper outer, lower inner, lower outer
- AJCC Stage
- Tumor Size

13.0 Treatment/Follow-up Decision at Evaluation of Patient

Follow-up data will be collected and entered after the observation phase outlined in section 4.0. If the patient is still alive after 5 years have elapsed from the on-study date, no further follow-up is required by this protocol.

- 13.1 Patients who have a recurrence while receiving therapy or during observation will go to the event-monitoring phase and be followed
- 13.2 Patients who discontinue treatment or observation for reasons other than recurrence will go to the event-monitoring phase and be followed
- 13.3 Patients who will not receive any radiation treatment or who will receive radiation treatment elsewhere will move to event monitoring phase.
- 13.4 A patient is deemed *ineligible* if after registration, it is determined that at the time of registration, the patient did not satisfy each and every eligibility criteria for study entry. The patient may continue treatment off-protocol at the discretion of the physician as long as there are no safety concerns, and the patient was properly registered. The patient will go directly to the event-monitoring phase of the study (or off study, if applicable).

If the patient received treatment, all data up until the point of confirmation of ineligibility must be submitted. Event monitoring will be required per Section 18.0 of the protocol.

- 11.5 A patient is deemed a *cancel* if he/she is removed from the study for any reason before any study treatment is given. On-study material and the End of Active Treatment/Cancel Notification Form must be submitted. No further data submission is necessary.

14.0 Body Fluid Biospecimens

- 14.1 Summary Table of Research Blood and Body Fluid Specimens to be Collected for this Protocol

Collection Tube	Volume to Collect per Tube (Number of Tubes to Collect)	Timepoint: Last day of treatment (+/- 2 days)	Timepoint: 12 weeks post-radiation (+/- 2 days)	Timepoint: 12 months post-treatment visit (+/- 3 months)
EDTA tubes	10 mL (1)	X	X	X
No additive tubes (for Serum)	10 mL (1)	X	X	X

The baseline sample will be obtained through co-enrollment in Radiation Oncology Patient Outcomes Registry and Biobanking Study, IRB#15-00136. All other samples will be drawn according to the test schedule and summary table above. Collect and process last day of treatment, 12 weeks post-radiation, and 12 months post-treatment, blood/blood products according to table 14.1. Label specimen tube(s) with protocol number, study patient ID number, and time and date blood is drawn.

- 14.2 BAP will process and store specimens per standard operating procedures.
- 14.3 Bloods will be collected prospectively and stored until funding sources have been

secured to investigate exploratory analyses described in section 16.64

15.0 Drug Information

Not Applicable

16.0 Statistical Considerations and Methodology

This is an open label phase II randomized controlled trial to determine the safety of 15 fraction vs 25 fraction scanning beam proton radiotherapy after mastectomy in patients requiring regional nodal irradiation.

16.1 Primary Endpoint:

16.1.2 Primary endpoint: 24 month complicate rate, defined as the percentage of women randomized who develop one or more of the following events:

- 1) grade 3 or higher late adverse events
- 2) unplanned surgical intervention (not including planned serial fat grafting) in patients who undergo mastectomy with reconstruction.

16.2 Secondary Study Endpoints: The secondary aims of this study are to characterize acute and late adverse events including grade ≥ 2 pneumonitis and reconstruction failure rate, assess patient self-reported cosmesis, evaluate fatigue, breast pain, arm function and other patient reported outcomes, compare the locoregional control, disease free, overall survival. Blood will be collected for future studies exploring dose volume and genomic predictors of adverse cosmesis and biomarkers of cardiotoxicity.

The following definitions are used for the secondary endpoints of interest:

- *Acute adverse events* (up to 90 days post-RT): any adverse event, regardless of attribution, that occurs in the first 90 days post-RT.
- *Late adverse events* (up to 5 years post XRT): any adverse event that occurred after the first 90 days post-RT and up to 5 years post-RT.
- *Reconstruction failure* (up to 5 years post XRT): loss of the tissue expander or implant with the inability to replace it resulting in no final reconstruction or conversion to autologous reconstruction or revised with the addition of autologous reconstruction.[27, 28]
- *Patient Reported Outcomes/Quality of life*: Elements of the Patient-Reported Outcomes Version of the Common Terminology Criteria for Adverse Events (PRO-CTCAE) will be used for patient self-reporting of toxicities. The Breast Cancer Treatment Outcomes Scale (BCTOS) will be used to measure patient reported functional status (pain, mobility). Other measures of fatigue, pain, and arm function are listed in the appendix.
- *Patient self-reported cosmetic outcomes*: the patient self-reported outcome will be assessed using a modified Harvard Cosmesis Scale and a modified BCTOS at baseline, 2 years, and 5 years.
- *Panel assessed cosmetic outcome*: in addition to patient self-reported and physician reported outcomes, cosmesis will be assessed by a panel of breast cancer medical providers using digital photographs from baseline and at 2 years. The Panel will be blinded to treatment allocation.

- *IBTR*: this is defined as local recurrence from trial registration as a first event at 5 years. IBTR is defined as both invasive and non-invasive breast cancer involving the same breast parenchyma as the original tumor.
- *Regional recurrence*: invasive breast cancer in the axilla, regional lymph nodes, chest wall, and skin of the ipsilateral breast at 5 years.
- *Distant recurrence*: metastatic cancer that has either been biopsy confirmed or clinically diagnosed as recurrent invasive breast cancer at 5 years.
- *Invasive disease free survival*: this is defined as the time from study registration until the occurrence of one of the events in a composite endpoint. This endpoint includes invasive IBTR, regional invasive breast cancer recurrence, distant breast cancer recurrence, death due to any cause, contralateral invasive breast cancer, and second primary non-breast invasive disease.
- *Overall survival*: is defined as the time from registration to death due to any cause.

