1.2 Rationale for Proton Therapy in Breast Cancer

Relative to photons, protons have fundamental physical advantages in the treatment of tumors adjacent to radiosensitive normal structures. By exploiting the Bragg peak of proton beams, clinicians are able to achieve a dose distribution to target tissues similar or better to that accomplished with photons, while reducing unintended dose to nearby normal structures[11, 12]. Thus, interest in the possible benefits of breast cancer radiotherapy with protons is emerging, with hopes of being able to maintain or improve the locoregional control and cause-specific survival with the addition of photon radiation, while reducing toxicity.

MacDonald et al [13] recently published early outcomes for a small cohort of 12 patients treated with proton radiotherapy following mastectomy. All patients received chest wall irradiation and eleven received radiotherapy to the supraclavicular, level 3, and internal mammary lymph node chains. Five of the 12 women had permanent implants at the time of radiotherapy. Nine patients had grade 2 skin toxicity and 3 patients had grade 1 skin toxicity. There was no \geq grade 3 skin toxicity reported. During treatment 6 patients experienced grade 1 fatigue, 5 patients experienced grade 2 fatigue, and there was one incident of grade 3 fatigue. By 4 weeks follow-up fatigue had completed resolved in all but 1 patient who continued to have grade 1 fatigue. There were no reported cases of pneumonitis. The average mean dose to the heart was 0.44 Gy and the average mean V20 of the lung was 12.7%. Cuaron et al. recently reported the results of treatment of the largest cohort of patients treated with proton therapy for breast cancer.[14] Four patients were treated after lumpectomy, 24 after mastectomy (including 14 patients with implant reconstruction and 1 patient with autologous reconstruction) and 2 patients received proton therapy after wide local excision of a chest wall recurrence. Grade 2 dermatitis occurred in 20 patients (71.4%), 8 of whom (28.6%) also experienced moist desquamation. Grade 2 esophagitis was observed in 8 patients (28.6%). There was 1 grade 3 reconstructive complication. The median mean heart dose was 0.88Gy and the median V20 of the ipsilateral lung was 16.5%. This early data suggests that post-mastectomy proton therapy is feasible and associated with reduced dose to the heart and lung, warranting further study.

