2.2 Secondary

2.2.1 To evaluate acute and late toxicity

2.2.2 To evaluate the rate of reconstruction failure (defined as loss of the tissue expander or implant with the inability to replace it resulting in no final reconstruction or conversion to autologous reconstruction or unplanned revision with the addition of autologous reconstruction).[27, 28]

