3.0 Patient Eligibility

3.1 Inclusion Criteria

- 3.12 Age \geq 18 years
- 3.13 Histologic confirmation of breast cancer resected by mastectomy with or without immediate reconstruction and chest wall and regional nodal irradiation planned.
- 3.14 pStage T1-T4N0-N3M0 or ypStage T0-4N0-N3M0
Note: The axilla must be staged by sentinel node biopsy alone, sentinel node biopsy followed by axillary node dissection, or axillary lymph node dissection alone
- 3.15 ECOG Performance Status (PS) 0 to 2. (Appendix I).
- 3.17 Radiotherapy must begin within 12 weeks of last surgery (breast or axilla) or last chemotherapy.
Note: Breast implants and expanders allowed
- 3.18 Able to and provides IRB approved study specific written informed consent
- 3.19a Ability to complete questionnaire (s) by themselves or with assistance
- 3.19b Able to complete all mandatory tests listed in section 4.0
- 3.19c Willing to return to enrolling institution for follow-up (during the active monitoring phase of the study)
- 3.19d Willing to provide tissue and blood samples for correlative research purposes.
- 3.19e Rochester and Arizona patients: Willing to sign consent onto the Mayo Clinic Radiotherapy Patient Outcomes Registry and Biobanking study, IRB number 15-000136
- 3.30 Rochester patients: Willing to sign consent onto Evaluation of cardiac function in patients undergoing proton beam or photon radiotherapy, IRB number 15-007443

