7.71 Post-mastectomy chest wall and regional node target volumes (Arms 1 and 2)

Post-mastectomy chest wall and regional node CTV: Includes the chest wall, along with all 3 levels of the axilla, supraclavicular lymph nodes, and internal mammary lymph nodes. The chest wall contour is based on anatomical borders of the chest wall from the RTOG Breast Cancer Atlas but not extending deeper than the anterior surface of the ribs and intercostal muscles except in the vicinity of the internal mammary lymph nodes. The chest wall is also limited anteriorly to exclude the first 3 mm of tissue under the skin. In general, the chest wall CTV should include the mastectomy scar but not cross midline. Expanders, implants, or autologous tissue present for reconstruction is allowed and at least the most peripheral 1 cm should be included in the post-mastectomy chest wall and regional node CTV. In patients with subpectoral implants the implant may be excluded only with permission from the principal investigator or representative. The 3 levels of the axilla should generally follow the RTOG-endorsed consensus guidelines, although the superior border of level II of the axilla should extend to the most cranial CT-slice of the axillary vessels and [30] both the medial and lateral supraclavicular lymph nodes should

be included (Brown et al IJROBP 2015), as described by Dijkema and colleagues.[30] In addition, the internal mammary lymph nodes will be defined as the region of the internal mammary vessels plus an approximate 5 mm medial and 5 mm lateral margin, limited medially by the sternum and posteriorly by the lung and heart. The internal mammary lymph nodes should extend from the cranial CT-slice of the 4th rib to the cranial CT-slice of the jugulo-subclavian junction.[30]. The internal mammary lymph node structure should be incorporated into the CTV but it will also have its own separate individual constraints.

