16.62 Secondary Analyses

16.621 *Acute adverse events (up to 90 days post-RT):* All patients who were registered to the study and started treatment will be included in the acute adverse event analysis. An acute adverse event is an AE, regardless of attribution, that occurs up to 90 days post-RT. The maximum grade for each type of acute AE will be recorded for each patient. Data will be summarized as frequencies and relative frequencies by treatment arm. Additionally, the relationship of the adverse event(s) to the study treatment will be taken into consideration.

16.622 *Late adverse events and reconstruction failure:* All patients who were registered to the study and started treatment will be included in the late adverse event and reconstruction failure analysis. A late adverse event is an AE, regardless of attribution, that occurs at least 90 days post-RT and up to 5 years post-RT. The maximum grade for each type of late AE will be recorded for each patient. Data will be summarized as frequencies and

relative frequencies by treatment arm. Additionally, the relationship of the adverse event(s) to the study treatment will be taken into consideration.

- 16.623 *Quality of life*: The subscales of the BCTOS, elements from CTCAE-PRO, and other patient reported measures such as fatigue, breast pain, breast shape, and arm related morbidity outlined in the appendix will be summarized as the mean \pm SD and median (minimum value, maximum value). Changes in the QOL measurements from baseline will be determined at each follow-up visit and measured by treatment arm. The comparison of the changes at each time point between the two treatment arms within each cohort will be done with a paired t-test or Wilcoxon signed rank test, whichever is appropriate.
- 16.624 *Cosmesis*: The values of the cosmesis instruments (patient self-reported and panel-assessed) will be summarized with the frequencies and confidence intervals of fair or poor cosmesis events at baseline, 2 years, and 5 years by treatment arm.
- 16.625 *IBTR incidence*: The IBTR cumulative incidence will be estimated using a competing risks method (Gooley et al.) by treatment arm. The competing risks will be regional/distant breast cancer recurrence and death.

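### Reconstruction failure is built on loss of an expander or implant, but women with autologous flaps and women without reconstruction stay in its denominator, so some flap losses go uncounted and the reported rate is lowered

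*Combined protocol and SAP*

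**What the plan says.** The endpoint is defined twice. Section 2.2.2 has it "defined as loss of the tissue expander or implant with the inability to replace it", and section 16.2 opens in the same way: "loss of the tissue expander or implant with the inability to replace it resulting in no final reconstruction or conversion to autologous reconstruction". Each continues with a third limb. In 16.2 it reads "or revised with the addition of autologous reconstruction"; in 2.2.2 it is "unplanned revision with the addition of autologous reconstruction", so only 2.2.2 requires the revision to be unplanned. Neither section names loss of a flap.

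The trial is not limited to device-based reconstruction. Section 3.13 requires disease "resected by mastectomy with or without immediate reconstruction" and excludes no type. Section 7.71 says "Expanders, implants, or autologous tissue present for reconstruction is allowed".

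The analysis population is in 16.622: "All patients who were registered to the study and started treatment will be included in the late adverse event and reconstruction failure analysis". Results are frequencies by arm, with no test. Section 11.4 has a plastic surgeon and a general surgeon adjudicate the endpoint but gives them no rule for flaps. Section 5.1 balances the arms on whether there was immediate reconstruction, not on its type.

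**The concern.** The event and the population do not match. The event starts from a device, while the population includes women who have no device to lose. Two things follow.

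- **Uncounted events.** A woman whose immediate flap is lost and who ends with no reconstruction has the outcome that the definition aims at, yet she does not meet it. The same holds if the flap is replaced by an implant.
- **Dilution.** Women with flaps, and women with no reconstruction, enlarge the denominator and add few or no events. The reported percentage is then neither the failure rate of device-based reconstruction nor that of reconstruction overall.

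The rate is what a reader will use to judge whether the shorter schedule is compatible with reconstruction, and to compare with published series. The definition cites references 27 and 28, whose titles concern expanders and implants. A rate computed on a mixed denominator would look better than those series partly through its construction.

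**Working it through.** **The plan's own figures.** The plan gives no rate, sample size or power for reconstruction failure. Its only sizing figures are the primary endpoint's power, 80% (10% vs 5%) and 41% (10% in both arms), in 16.4. With 36 per arm and an unpooled one-sided 95% upper limit against the 10-point margin, exact enumeration gives 79.4% and 41.7%, so they reproduce. They do not bear on this point.

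**Which outcomes after a flap count?**

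| Outcome for a woman with a flap | Device-loss limbs | Third limb |
|---|---|---|
| Lost, not replaced | No | No |
| Lost, replaced by an implant | No | No |
| Revised with further autologous tissue | No | Possibly, if the limb is read on its own |

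**Inputs**
- Evaluable patients: 72 (16.4), so 36 per arm.
- Share reconstructed: about 2/3 (16.4), so 72 x 2/3 = 48, or 24 per arm.
- Autologous share of reconstructed women, f: not given. The only pointer is a cited proton cohort (1.2) with "14 patients with implant reconstruction and 1 patient with autologous reconstruction", that is 1/15 = 6.7%. Shares from 0 to 50% are shown as assumptions.
- Failure rate among device patients, r: not given. 10% is assumed for illustration.

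**Number of flap patients.** 48 x 1/15 = 3.2 and 48 x 0.30 = 14.4, so about 3 to 14 women in the trial, or 1.6 to 7.2 per arm.

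**Dilution.** Taking flap patients to add no events:
- rate among reconstructed women = r x (1 - f)
- rate on the 16.622 population = r x (1 - f) x 2/3

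| f | Among reconstructed women | All treated women (16.622) |
|---|---|---|
| 0 | 10.0% | 6.7% |
| 1/15 | 9.3% | 6.2% |
| 20% | 8.0% | 5.3% |
| 30% | 7.0% | 4.7% |
| 50% | 5.0% | 3.3% |

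The relative reduction from flaps is f itself: 7% at 1/15 and 30% at 30%, whatever r is. The factor 2/3 for women without reconstruction is the larger reduction whenever 1 - f > 2/3, that is for any f below 1/3. With numerator and denominator both limited to device patients, the rate is 10% for every f.

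**Uncounted flap losses.** The flap-loss rate is also not given. If it equalled the assumed 10%, the uncounted women per arm would number 1.6 x 0.10 = 0.16 to 7.2 x 0.10 = 0.72, fewer than one.

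**The case against.** The strongest reply is that the device focus is deliberate. The cited sources concern devices, section 1.3 calls it critical to learn whether hypofractionation is feasible with immediate implant-based reconstruction, and the note under 3.17 names only implants and expanders. Adding flap loss to the definition would weaken comparability with those sources. This stands, and it is why the remedy keeps the device definition. It does not excuse the denominator: if the endpoint concerns devices, 16.622 should be limited to women who have one.

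Several stronger readings are tempting, and the documents do not support them.

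- A reader might infer that a flap patient can never be a failure. The third limb, read on its own, could count one who is revised with further autologous tissue.
- A reader might infer that flap loss disappears from the trial. The primary endpoint in 16.1 counts unplanned surgery after any reconstruction, so a flap loss that leads to such surgery within 24 months is a primary event. A later loss, or one without surgery, is not captured by that component, and the secondary label is missing in every case.
- A reader might take the 15% in 16.4 as the device failure rate. It refers to unplanned surgical complications after immediate reconstruction, which is a different event.
- A reader might infer that many flaps are expected. Section 7.71 only allows them.
- A reader might infer a bias between arms. Randomisation balances reconstruction type in expectation. Chance imbalance is possible because type is not a balancing factor, but that is true of any unbalanced factor in a small trial, and no test or decision uses this endpoint.

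**Conclusion.** The point holds as a minor mismatch between definition and denominator. Followed as written, 16.2 and 16.622 leave uncounted a flap that is lost and not replaced, or is replaced by an implant, and they keep flap patients and unreconstructed women in the denominator. The rate among reconstructed women falls by about f in relative terms (7% at 1/15, 30% at an assumed 30%), and the 16.622 population multiplies it by about a further 2/3.

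The relative sizes rest on f, which the documents do not give, on the planning figure of about 2/3 reconstructed, and on flap patients adding no events. The absolute percentages also rest on the assumed 10% device failure rate. The primary analysis, the sample size and the decision rule are not affected.

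**What to change.** 1. In 16.2 and 16.622, limit both numerator and denominator of reconstruction failure to women with expander- or implant-based reconstruction. This also removes women without reconstruction from the denominator.
2. Use one wording in 2.2.2 and 16.2, and state whether a planned revision with autologous tissue counts; at present only 2.2.2 requires the revision to be unplanned.
3. Report women with autologous reconstruction in a separate row by arm, with total loss or removal of the flap as their failure event, judged by the adjudicators already named in 11.4.

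The cost is a slightly smaller denominator and one extra descriptive row. Section 18.1 lists a Breast Reconstruction form among the initial materials, which may supply the type of reconstruction. Its fields are not shown, and a baseline form cannot record a later loss, so the team should confirm that follow-up data capture flap loss.

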2.2.3 To determine the 5-year locoregional control, disease free survival and overall survival

- 2.24 To evaluate fatigue, arm function, and other patient reported outcomes
- 2.25 To evaluate clinical features, treatment technique, dose-volume parameters, histologic and genetic variants associated with fair and poor cosmetic outcome or unplanned surgical intervention.
- 2.26 To compare echocardiographic changes, including left ventricular strain pattern, between fractionation regimens

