11.0 Treatment Evaluation

11.1 Patients will be evaluated at baseline, then according to the Assessment Schedule (Section 4.0)

11.2 At the time of reevaluation, patients will be classified in the following manner:

11.2.1 No evidence of disease (NED).

11.2.2 Recurrence of disease (REC). Recurrence must be confirmed by biopsy.

11.2.3 The site of recurrence (or failure) will also be collected and classified as local vs. regional vs. distant recurrence. The specific site of failure will also be collected as well.

11.2.4 Secondary Treatment. The date of the first retreatment and extent of retreatment post-recurrence (i.e. secondary resection or re-irradiation for primary disease), will be collected. Pathology, if available, and operative reports are required to be submitted per Section 18.0.

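### In a mastectomy-only trial, the sole local-recurrence endpoint is confined to breast parenchyma, and the 5-year locoregional control aim has no defined composite, estimate or interval

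*Combined protocol and SAP*

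**What the plan says.** Eligibility (section 3.13) requires "Histologic confirmation of breast cancer resected by mastectomy with or without immediate reconstruction", and the irradiated target in 7.71 includes the chest wall.

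The goals include (2.2.3) "To determine the 5-year locoregional control, disease free survival and overall survival". Section 16.2 repeats the aim as a comparison: "compare the locoregional control, disease free, overall survival".

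The definitions in 16.2 contain no locoregional endpoint. The only local one is IBTR. Its event and timing are given as "this is defined as local recurrence from trial registration as a first event at 5 years", and its tissue as "IBTR is defined as both invasive and non-invasive breast cancer involving the same breast parenchyma as the original tumor". Regional recurrence is "invasive breast cancer in the axilla, regional lymph nodes, chest wall, and skin of the ipsilateral breast at 5 years".

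Sections 16.625 to 16.627 estimate separate cumulative incidences by arm for IBTR, regional and distant recurrence. Each lists the other recurrence types and death as competing risks, and none mentions a confidence interval or a between-arm comparison. Among the disease outcomes, 95% CIs are specified only for disease-free and overall survival (16.628, 16.629).

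On data collection, section 11.2.3 states "The site of recurrence (or failure) will also be collected and classified as local vs. regional vs. distant recurrence" and then "The specific site of failure will also be collected as well". It does not say what local or regional means for a patient without a breast.

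**The concern.** The IBTR definition belongs to breast conservation. In this trial the chest wall is treated in every patient, and whether the shorter schedule controls disease there is a natural question for the local endpoint. As defined, that endpoint can register only cancer in residual breast tissue. Most chest-wall failures would appear under a regional label, and one type would appear under no label.

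The stated aim also has no matching analysis. A reader of the final report would look for 5-year locoregional control by arm with an interval. The plan would supply two separate incidences without intervals and no rule for combining them. Any composite would then have to be defined after the data are in, in an open-label trial.

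**Working it through.** The point rests on definitions, so the first step sets them side by side. The plan states no figure for locoregional control, so there is none to reproduce.

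**Step 1. Where each type of first recurrence falls under 16.2, applying the parenchyma sentence.**

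- Invasive or non-invasive, in residual breast tissue: IBTR.
- Invasive, in the chest wall or ipsilateral skin: regional.
- Invasive, in the axilla or other regional nodes: regional.
- Non-invasive, in the chest wall or skin outside residual parenchyma: neither.

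The lumpectomy wording in 7.2 does not restore a role for IBTR, because eligibility admits mastectomy only.

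**Step 2. What can be derived for locoregional control.** IBTR and regional recurrence are listed as competing with each other, and both compete with distant recurrence and death. Their 5-year cumulative incidences therefore add:

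CI(locoregional) = CI(IBTR) + CI(regional).

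This gives a point estimate of first-event locoregional failure. It covers all invasive events but omits the fourth type in Step 1.

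**Step 3. Expected event numbers.** Section 16.4 plans to treat 82 patients at 1:1, so 82/2 = 41 per arm. The documents give no 5-year locoregional rate for this population. Section 1.3 cites local-regional relapse of 4.3% to 8.8% from the START trials at 10-year follow-up, and notes that few of those patients had a mastectomy or nodal irradiation.

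- At the cited rates: 41 × 0.043 = 1.8 to 41 × 0.088 = 3.6 events per arm.
- Over a wider assumed range of 2% to 10%: 41 × 0.02 = 0.8 to 41 × 0.10 = 4.1 events per arm.

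**Step 4. Why an interval cannot be had by adding limits.** Exact (Clopper-Pearson) 95% limits for x events in n patients are the 2.5% quantile of Beta(x, n − x + 1) and the 97.5% quantile of Beta(x + 1, n − x). For n = 41, assuming complete follow-up:

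- 0/41: 0% to 8.6%.
- 2/41 = 4.9%: 0.6% to 16.5%.
- 3/41 = 7.3%: 1.5% to 19.9%.

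Suppose an arm has 0 IBTR and 2 regional events. Adding the separate limits gives 0 + 0.6 = 0.6% and 8.6 + 16.5 = 25.1%. The composite of 2/41 has limits of 0.6% to 16.5%. The point estimate is the same, 4.9%, but the summed upper limit is 8.6 points too high. The composite therefore needs its own planned interval.

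**Step 5. The non-invasive gap.** If an arm had 2 invasive locoregional events and 1 non-invasive skin recurrence outside residual tissue, the sum as written would be 2/41 = 4.9%. A composite that includes in situ events would be 3/41 = 7.3%. The documents give no frequency for such events, so this shows only the effect of one event.

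**The case against.** The strongest reply is that little is lost. An invasive chest-wall event counts once in the locoregional total whether it is called local or regional, and it counts in invasive disease-free survival through the regional term. A non-invasive one could still count in disease-free survival under 16.628, which is not limited to invasive recurrence. Whether the chest wall is labelled local or regional is partly convention. The expectation that IBTR will be very low is inferred from the definition and is not a figure in the documents. All of this stands, and it limits the weight of the point. It does not supply the missing composite or its interval, and it does not make IBTR informative about the chest wall.

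Two stronger readings are tempting and are not supported.

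- A reader might infer that a chest-wall failure recorded as local under 11.2.3 would be counted in both IBTR and regional recurrence. That requires ignoring the second IBTR sentence, the explicit listing of the chest wall under regional recurrence, and the competing-risk structure of 16.625 and 16.626. What remains is that 11.2.3 leaves its classes undefined and should be aligned with 16.2.
- A reader might infer that an arm difference in chest-wall failure would be concealed. The specific site of failure is collected and the two first-event incidences add, so such a difference could be recovered. It is absent from the planned summaries, not from the data.

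**Conclusion.** The point holds as a mismatch between population, endpoint definition and stated aim. Following 16.2 as written gives a local-recurrence result that largely cannot register failure in the irradiated chest wall, leaves non-invasive chest-wall or skin recurrence outside both endpoints, and provides no planned estimate or interval for 5-year locoregional control.

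Its weight is moderate: it should be corrected, but it does not threaten the trial. These are secondary, descriptive endpoints with roughly 1 to 4 expected locoregional events per arm, assuming a 5-year rate of 2% to 10% and 41 treated per arm. At those numbers any interval will be wide, and nothing here implies that a conclusion about the two schedules would change. The primary endpoint, power and sample size are unaffected. The numerical illustrations ignore censoring and competing deaths.

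**What to change.** - In 16.2, replace IBTR with local recurrence: invasive or in situ cancer in the ipsilateral chest wall, overlying skin, scar, reconstructed breast or residual breast tissue.
- Limit regional recurrence to the ipsilateral regional nodes.
- Define locoregional recurrence as the first of either. Count simultaneous local and regional events once in the composite, and state how they are handled in the separate local and regional analyses.
- In 16.62, add the 5-year cumulative incidence of locoregional recurrence by arm with a 95% CI, with distant recurrence and death as competing events. Treat any between-arm difference as descriptive.
- Align the competing-risk lists in 16.625 to 16.627, the component list for invasive disease-free survival in 16.2, and the site classes in 11.2.3.

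The cost is protocol and SAP wording. Because 11.2.3 already collects the specific site of failure, chest-wall events can be reclassified without new data. The change should be made before the 5-year analysis.
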